5.4.3 Deviation from Protocol

Influenza and COVID-19 vaccine may be administered outside of study window in case of public health emergency or personal exposure.

5.5 Data Collection

5.5.1 Participant Demographics and Vaccine History

5.5.1.1 Enrollment questionnaire administration

Research staff will administer the enrollment questionnaire or participants may complete electronically. Data will be recorded electronically directly into a data management system such as REDCap.

5.5.1.2 Enrollment questionnaire content

Each participant/participant's LAR(s) will be interviewed to collect information on patient demographics, influenza and COVID-19 vaccination history, and self-reported lab-confirmed influenza or COVID-19 infection in the previous 90 days. Any modifications or additional questions will be submitted for IRB approval before inclusion on enrollment questionnaires. Participant height and weight information may be collected at one of the first three study visits.

5.5.2 Follow-up Surveillance for Vaccine Reactogenicity and Safety and Self-Reported ARI or Change in Health Status Resulting in Hospitalization

5.5.2.1 Follow-up Survey (Reactogenicity)

Participants will complete a brief survey regarding vaccine reactogenicity and safety data 3 days after receipt of either vaccine dose administered according to study procedure (day 0 [groups i-iii] and day 28 [groups ii and iii]).

Follow-up surveys will be completed online. Participants will receive an automated link to an electronic survey 3 days after receipt of either vaccine dose administered according to study procedure (day 0 [groups i-iii] and day 28 [groups ii and iii]) via their preferred contact method (text or email). Participants will complete the survey a maximum of two times during the study period. The first survey will be sent 3 days after Visit 1 (groups i-iii) and the second survey will be sent 3 days after Visit 2 (groups ii and iii). If the survey has not been completed, up to 3 reminder notifications will be sent to the preferred contact method each week.

5.5.2.2 Follow-up Survey (ARI)

Participants will complete a brief survey regarding absence/presence of new ARI symptoms, illness test results (if applicable) and change in health status requiring hospitalization each week.

Weekly surveys will be completed online. Participants will receive an automated link to an electronic survey each week via their preferred contact method (text or email). Participants will complete the survey once per week. The first survey will be sent 7 days after Visit 1 (day 0) and will be sent out each week until the end of the study period (Visit 4; day 180). If the survey has not been completed, a reminder notification will be sent to the preferred contact method each week.

5.5.2.3 Qualifying ARI Definition

An ARI during follow up is defined as an illness with new onset in the past 7 days and any two of the following symptoms: cough, fever or feeling feverish/chills, sore throat, runny/stuffy nose, muscle or body aches, headache, fatigue (tiredness), nausea or vomiting, diarrhea, new loss of smell or taste, or shortness of breath or difficulty breathing.

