Demographic and health data (including influenza and COVID-19 vaccination and infection history) will be collected upon enrollment and verified after enrollment via electronic medical record extraction. Enrolled participants will be randomized to one of the following interventions (2:1:1) using a permuted block method stratified by age group (aged 6-11 years and 18-64 years) and site: (i) concomitant administration of the mRNA COVID-19 vaccine (Moderna) and quadrivalent influenza vaccine (cclIV4); (ii) sequential administration of the quadrivalent influenza vaccine (cclIV4) at Visit 1 (day 0) and the mRNA COVID-19 vaccine (Moderna) at Visit 2 (day 28); (iii) sequential administration of the mRNA COVID-19 vaccine (Moderna) at Visit 1 (day 0) followed by the quadrivalent influenza vaccine (cclIV4) at Visit 2 (day 28). Whole blood samples to isolate sera, PBMC and plasma (target to collect PBMC and plasma samples at every visit from a subset of 250 participants; 200 adults and 50 children) will be collected prior to vaccination administration at Visit 1 (day 0) and Visit 2 (day 28). Participants will not be blinded to vaccine group and will receive two vaccines in separate limbs (for the concomitant vaccination [group i]) or one vaccine at Visit 1 (day 0) and a second vaccine at Visit 2 (day 28) (for sequential vaccination [groups ii and iii]) in an unblinded manner.

Participants will provide a blood sample for isolation of serum, PBMC, and plasma (target to collect PBMC and plasma samples at every visit from a subset of 250 participants; 200 adults and 50 children) at Visit 3 (day 56; post-vaccination 2) and Visit 4 (day 180; end of local flu circulation). If participants exhibit ARI during the study period, they may be asked to present for

an acute (<10 days after symptom onset) and convalescent (28 days after acute visit) visit to provide a nasal swab for viral testing (acute visit only) and blood sample for isolation of serum, PBMC, and plasma (acute and convalescent visit for those with positive viral molecular test for influenza or SARS-CoV-2). Influenza virus and SARS-CoV-2 serologic and cellular immunity testing will be conducted at CDC and/or a CDC-approved site.

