5.7.2.1 In-system sources/electronic medical records

Each study site will query the health system's electronic medical record system to obtain prior season influenza and COVID-19 infection data for all participants regardless of self-reported prior infection status. Prior influenza and COVID-19 infection history data may include records from multiple prior seasons from electronic health records.

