## 6.3 Influenza Immunogenicity Population

The Influenza Immunogenicity Population is a subset of the mITT Population that includes only subjects who received both vaccines, provide visit 1 and visit 2 blood draws available with HAI titer results for analysis within the protocol-defined time frame, did not have an influenza or SARS-CoV-2 infection between visits 1 and 2, and had no protocol violations affecting immunogenicity. Protocol violations affecting the immunogenicity analyses are defined in the Statistical Analysis Plan (SAP) Appendix 1. The acceptable visit window for sample analysis will be +14 days from the target date. Should 10% or more of the total study population be excluded from the Influenza Immunogenicity Population due to missing the visit window, then an additional analysis will be performed including these subjects with the missing visit window exclusion.

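### A 7-day symptom look-back on a weekly survey with no catch-up leaves no slack, so an illness that starts in a skipped week may go undetected, and the SAP does not say what establishes infection

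*Protocol*

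**What the plan says.** - **Definition.** Protocol 5.5.2.3: "An ARI during follow up is defined as an illness with new onset in the past 7 days", with any two symptoms from a list.
- **Survey.** Protocol 5.5.2.2: "The first survey will be sent 7 days after Visit 1 (day 0) and will be sent out each week" until Visit 4. For non-response: "If the survey has not been completed, a reminder notification will be sent to the preferred contact method each week". No catch-up question or longer look-back is stated. The same survey also asks for illness test results, with no stated recall period.
- **Acute and convalescent sampling.** Protocol 5.1 provides for "an acute (<10 days after symptom onset) and convalescent (28 days after acute visit) visit", and Table 2 in 5.4.1 gives the same limits.
- **Trigger.** Protocol 3.2 offers specimens to those reporting *qualifying* ARI symptoms, and Table 2 is titled for *qualifying* events. The acute-visit text in 5.4.1 refers to reported ARI symptoms without that word.
- **Records.** Protocol 5.7.2 covers documented influenza and COVID-19 infection through the end of the study. Section 5.7.2.1 has each site query its health system's "electronic medical record system to obtain prior season influenza and COVID-19 infection data" for all participants, whatever they self-report. For vaccination there is also a subsection on external sources (5.7.1.2). For infection there is none.
- **Analysis.** SAP 6.3 keeps only participants who "did not have an influenza or SARS-CoV-2 infection between visits 1 and 2", and SAP 6.4 applies the same condition. Neither says which source establishes infection. Missed surveillance is not among the violations in SAP Appendix 1.

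**The concern.** The look-back and the survey interval are both 7 days, so the scheme covers every onset day only if every survey is answered on time or nearly so. A skipped survey leaves a hole that the next survey, on the written definition, does not fill.

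Two uses of the data are exposed. The SAP 6.3 and 6.4 populations are meant to exclude people infected between Visits 1 and 2, whose Visit 2 titres may reflect infection as well as vaccination. An infection that nobody detects cannot be excluded. The infection parts of EO5 and EO6 need acute and convalescent samples, and those cannot be recreated later from records.

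The two time limits also do not fit together. An illness that began 8 or 9 days before the survey is answered fails the definition but falls inside the acute-visit limit.

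**Working it through.** The documents give no infection rate, survey-completion rate or power figure on this point, so there is no stated figure to reproduce.

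**1. Which onset days are covered.** Take surveys due on days 7, 14, 21 and 28. The documents do not say what date the 7 days count back from; assume the day of answering. An onset is covered if a survey is completed 0 to 7 days later.

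| Situation | Onset days not covered |
|---|---|
| All on time | none |
| Day-14 survey skipped, next on day 21 | 8–13 (6 of 7) |
| Day-14 survey 1 day late | none |
| 2 days late | 8 |
| 3 days late | 8–9 |
| 4 days late | 8–10 |
| 6 days late | 8–12 |

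If onset exactly 7 days earlier does not count, the skipped week loses all 7 days (8–14), and a survey 1 day late loses day 8.

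**2. Against the acute-visit limit.** After the skipped survey, on day 21, onsets on days 12 and 13 are 9 and 8 days old and still within the limit. Onsets on days 8 to 11 are 13 to 10 days old and outside it. So 2 of the 6 lost days could still lead to an acute visit and 4 could not, before allowing time to arrange one. For a survey 2 or 3 days late, every lost onset is 8 or 9 days old, so the definition shuts out illnesses that the visit schedule would accept.

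**3. Share of onset days uncovered.** Let each survey be skipped independently with probability m (assumed). Six days of each week depend on one survey. The seventh is lost only if two surveys in a row are skipped. The share is (6m + m²)/7:

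- m = 5%: (0.30 + 0.0025)/7 = 4.3%
- m = 10%: (0.60 + 0.01)/7 = 8.7%
- m = 20%: (1.20 + 0.04)/7 = 17.7%
- m = 30%: (1.80 + 0.09)/7 = 27.0%

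With none skipped but answers 0 to 3 days late at random, the expected loss is 0.25 of 7 days (3.6%), or 0.625 of 7 days (8.9%) under the stricter day count.

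**4. Participants between Visits 1 and 2.** The primary contrast is group i against group ii (SAP 9.1). From the protocol summary, N = (300 + 100) + (150 + 50) = 600. Visit 2 falls on days 28 to 42, about 4 to 6 surveys. With infection rate q and miss rate m, both assumed:

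number affected = 600 × q × m × 6/7

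| q | m = 10% | m = 20% | m = 30% |
|---|---|---|---|
| 1% | 0.5 | 1.0 | 1.5 |
| 3% | 1.5 | 3.1 | 4.6 |
| 5% | 2.6 | 5.1 | 7.7 |
| 10% | 5.1 | 10.3 | 15.4 |

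That is 0.09% to 2.6% of 600, before any recovery through reported tests or records. The stricter day count replaces 6/7 by 1 and gives 0.6 to 18.

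**5. Illustration for the GMT ratio.** Suppose 2.57% of one group and none of the other were undetected influenza infections, each raising the titre 8-fold (2³; an assumption). The ratio would shift by a factor of 2^(0.0257 × 3) = 1.055. The one-sided split is deliberately unfavourable. The documents give no reason to expect it.

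**The case against.** **Infection status does not depend on the ARI definition.** A reader might infer that someone who falls ill in a skipped week is analysed as uninfected. Neither document says so. SAP 6.3 and 6.4 exclude on infection, not on a qualifying ARI, and survey-reported tests and record extraction are separate routes to it. The 7-day limit applies to symptom onset, and nothing confines the test-result question to that period. This stands: the consequence is possible, not automatic. These routes are still partial. Infection records are described only for the site's own system and only if recorded, while recruitment includes a volunteer registry, social media, students and employees, whom nothing shows to be tested there.

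**The definition may not bar an acute visit.** A reader might also infer that such an illness can never lead to sampling. The looser text in 5.4.1 could allow a visit on any reported ARI symptoms. But 3.2 and Table 2 say *qualifying*, so the protocol contradicts itself here and does not clearly permit the visit.

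**The survey form is not in the documents.** Whether a skipped week's link can still be answered, and over what period tests are asked about, cannot be judged. This also stands; the point is about the written rule.

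**A longer look-back recovers little acute sampling.** Correct: 4 of the 6 lost days after a skipped survey are past the acute-visit limit anyway, and EO5 and EO6 are exploratory. The gain is mainly in knowing infection status.

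**The loss falls on poor responders.** That follows from the definition and is not in itself evidence of bias. The surveillance is the same in all groups.

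**Conclusion.** The gap is real but limited. As written, a skipped weekly survey leaves 6 or 7 of that week's onset days unable to meet the definition at the next one, and an answer 2 or more days late loses part of the week. The 7-day and under-10-day limits, and the two wordings of the acute-visit trigger, are not reconciled. An illness missed this way may leave an infected participant in the SAP 6.3 and 6.4 populations, unless a reported test or in-system record reveals it.

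The effect on the primary analysis is probably small: about 0.5 to 15 of 600, before recovery. This rests on assumed infection rates of 1–10%, assumed miss rates of 10–30%, and counting onset exactly 7 days earlier as covered. The stronger conclusions, that every late survey loses illnesses, that affected participants are by rule classed as uninfected, or that the group i versus group ii comparison is biased, are not supported. The case for changing the plan is that the improvement is specific and cheap.

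**What to change.** - **Protocol 5.5.2.3 and the weekly survey.** Ask about onset since the last completed survey, or since Visit 1 if there is none. Record the onset date and any test date and result for that whole interval.
- **Protocol 3.2, 5.1, 5.4.1 (including Table 2) and 5.5.2.3.** Reconcile the 7-day definition with the under-10-day acute-visit limit, and use one wording for what triggers the visit.
- **SAP 6.3 and 6.4.** State that survey-reported tests, study swabs and record extraction together establish infection between Visits 1 and 2.

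The cost is a change to survey wording and logic, small protocol edits and a SAP sentence. The downside is longer recall for participants who skipped a survey. With the acute-visit limit unchanged, acute sampling for EO5 and EO6 is recovered only for onsets still under 10 days old.

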5.5.3 Study Product Supply, Storage, and Administration

In order to ensure adherence to study randomization assignment, age-appropriate, licensed quadrivalent cell culture-based influenza vaccines (ccIV4) and EUA or approved mRNA COVID-19 vaccine will be administered as a study procedure. Vaccines will be stored per manufacturer specifications.

5.5.3.1 Quadrivalent cell culture-based influenza vaccine

Flucelvax Quadrivalent (ccIV4) will be the designated study products for influenza vaccination. A standard-dose of ccIV4 contains 15 µg of HA per vaccine virus in a 0.5-mL dose. ccIV4 is approved for persons aged ≥6 months.

Vaccine lot numbers, dose, and site of vaccine administration will be recorded by research staff. After administration, used study syringes will be disposed of according to standard operating procedure.

Emergency management supplies including epinephrine (1:1000) and trained staff will be available for initial treatment of an allergic reaction, if needed.

5.5.3.2 mRNA COVID-19 vaccine

mRNA COVID-19 vaccine will be administered per FDA and ACIP recommendations. Study sites will work to coordinate the brand of mRNA vaccine administered based on recommendations and availability.

Vaccine lot numbers, dose, and site of vaccine administration will be recorded by research staff. After administration, used study syringes will be disposed of according to standard operating procedure.

Emergency management supplies including epinephrine (1:1000) and trained staff will be available for initial treatment of an allergic reaction, if needed.

5.5.4 Biospecimens Collection & Handling

5.5.4.1 Sera

Blood specimens for sera collection will be collected from participants at Visit 1 (day 0), Visit 2 (day 28), Visit 3 (day 56), Visit 4 (day 180), Acute Visit (<10 days after symptom onset), and Convalescent Visit (28 days after Acute Visit). Blood samples will be processed for sera, aliquoted, and stored at -20 C or colder at VE network laboratories until shipped to CDC for storage and subsequent testing via immunological assays to be performed at CDC and/or CDC-approved laboratory facilities (Laboratory Appendix B). We will collect 5-10 mL of whole blood for children aged 6-11 years and 10 mL of whole blood for adults aged 18-64 years. These volumes are preferred for sera processing, however, smaller volumes can be accepted if the situation does not allow for the collection of these amounts. The minimum accepted volume of whole blood to collect is 3 mL for all participants over the age of 6 years. Guidelines will be followed to ensure the amount drawn meets minimal risk criteria (i.e., 3 ml/kg in any 24-hour period, and 7 ml/kg in any eight-week period).

5.5.4.2 PBMC and Plasma

Blood specimens for PBMC and plasma collection will be collected from a subset of participants (target n=250; 200 adults and 50 children) at Visit 1 (day 0), Visit 2 (day 28), Visit 3 (day 56), Visit 4 (day 180), Acute Visit (<10 days after symptom onset), and Convalescent Visit (28 days after Acute Visit). Blood samples will be processed for PBMC and plasma, aliquoted, and stored at VE network laboratories until shipped to CDC for immunologic assays (Laboratory Appendix C). We will collect 8 mL (approximately 1 CPT tube) whole blood for children aged 6-11 years and 24 mL (approximately 3 CPT tubes) whole blood for adults aged 18-64 for PBMC and plasma processing. These volumes are preferred for PBMC and plasma processing,

however, smaller volumes can be accepted if the situation does not allow for the collection of these amounts. The minimum accepted volume of whole blood to collect for PBMC and plasma processing is 16 mL from adults between the ages of 18-64 and 5 mL for children between the ages of 6-11 years. Guidelines will be followed to ensure the amount drawn meets minimal risk criteria (i.e., 3 ml/kg in any 24-hour period, and 7 ml/kg in any eight-week period).

5.5.4.3 Nasal/Throat Swab

Sites may conduct respiratory testing for those that report ARI via the follow-up survey (ARI) during the study period via standard point of care respiratory testing for influenza and COVID-19.

5.6 Vaccine Safety and Reactogenicity

Participants will respond to an automated electronic survey 3 days following each vaccination visit to report the occurrence of fever, injection site reactions (pain, redness, swelling and itching) systemic reactions (chills headache, joint pain, muscle ache, body ache, fatigue, tiredness, nausea, vomiting, diarrhea, abdominal pain, rash lymph node swelling) the severity of reactions and their impact on health. Severity will be rated as mild (symptoms noticeable but aren't a problem) moderate (symptoms limit normal daily activities) or severe (symptoms make normal daily activities difficult or impossible). Impact on health will be assessed with respect to ability of the participant to attend work or school, ability to do normal daily activities and utilization of medical care.

The weekly automatic electronic survey will also request participants to report the occurrence of any change in health requiring hospitalization.

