- Obtain demographic and medical history including history of influenza and COVID-19 vaccination via enrollment questionnaire
- Take temperature and review temporary delay criteria
- Collect whole blood for sera sample (**Section 5.5.4.1**) and PBMC and plasma samples (in subset of participants, target n=250; 200 adults and 50 children) (**Section 5.5.4.2**)
- Randomize study participant to intervention (2:1:1) using a permuted block method stratified by site:
 - i. concomitant administration of the mRNA COVID-19 vaccine and quadrivalent influenza vaccine
 - ii. sequential administration of the quadrivalent influenza vaccine at Visit 1 (day 0) and the mRNA COVID-19 vaccine at Visit 2 (day 28)

- iii. sequential administration of the mRNA COVID-19 at Visit 1 (day 0) followed by the quadrivalent influenza vaccine at Visit 2 (day 28).
- Administer mRNA COVID-19 vaccine and/or quadrivalent influenza vaccine (Flucelvax [ccIV4]) based on randomization scheme
- Confirm date of next appointment at Visit 2 (day 28) of study

Follow-up Survey (Reactogenicity); 3 days after vaccine administration (Visits 1 and 2) – Vaccination Reactogenicity and Safety Data – Online Questionnaire

- Automated reminders sent to all participants to complete electronic survey via participant's preferred contact method approximately 3 days after receipt of either vaccine dose administered according to study procedure (day 0 [groups i-iii] and day 28 [groups ii and iii])
- Participants/participant's LAR(s) complete brief online survey regarding vaccine reactogenicity and safety data in the three days after receipt of either vaccine dose administered according to study procedure

Follow-up Survey (ARI); weekly following Visit 1 – Weekly ARI Surveillance and Change in Health Status – Online Questionnaire

- Automated reminders sent to all participants to complete electronic survey via participant's preferred contact method once per week beginning approximately one week after Visit 1 until completion of Visit 4
- Participants/participant's LAR(s) complete brief online survey regarding new ARI episodes and change in health status requiring hospitalization throughout the entire study period
- Participants that report new ARI may provide respiratory specimens for standard point of care respiratory testing and up to 2 additional blood draws (see Table 2: Schedule of Qualifying ARI Events)

Visit 2; study day 28 (28-42) – Specimen Collection and Vaccination 2 (groups ii and iii) – Clinic Visit

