5.7.2 Prior Lab-Confirmed Illness

All study sites will provide information for documented influenza and COVID-19 infection, if recorded, from January 1, 2020 through the end of the study period. The following data elements for prior infection will be collected for each lab-confirmed test if provided: date of test, type of test, result of test, and source of information.

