Two COVID-19 vaccine received Emergency Use Authorization (EUA) by the FDA in December 2020. BNT162b2 received FDA approval for individuals 16 years of age and older and mRNA-1273 received authorization for those 18 years of age and older. The Pfizer/BioNTech mRNA COVID-19 vaccine received additional EUA for adolescents 12 to 15 years in May 2021 and children 5 to 11 years in October 2021; both the Pfizer/BioNTech and Moderna mRNA COVID-19 vaccines received additional EUA for children aged down to 6 months in June 2022. The EUA was again updated to authorize the use of the updated bivalent vaccines as boosters for children aged down to 6 months in December 2022. These vaccines have been recommended at these ages by the ACIP.

Side effects that have been reported with mRNA COVID-19 vaccines include both injection site reactions as well as general side effects. Injection site reactions include: pain, tenderness and swelling of the lymph nodes in the same arm of the injection, swelling (hardness), and redness at the injection site. General side effects include: fatigue, headache, muscle pain, joint pain, chills, nausea and vomiting, fever and feeling unwell. There is a remote chance that an mRNA COVID-19 vaccine could cause a severe allergic reaction, usually occurring within a few minutes to hours after getting a dose of vaccine. Signs of a severe allergic reaction can include: difficulty breathing, facial and throat swelling, tachycardia, total body rash, dizziness and weakness. There have been rare reports of cases of inflammation of the heart—called myocarditis and pericarditis—happening after mRNA COVID-19 vaccination. The events have mainly occurred in adolescents and young adults and more often after the second dose of vaccine. Available data from short-term follow-up suggest that most individuals have had resolution of symptoms, but information is not yet available about potential long-term sequelae. These may not be all the possible side effects of the mRNA COVID-19 vaccines. Serious and unexpected side effects may also occur. mRNA COVID-19 vaccines are still being studied in clinical trials. Available data support the safety of dose 3 mRNA COVID-19 vaccine in immunocompromised individuals. Available data support the safety of booster doses of mRNA COVID-19 vaccine.

cclIV4 Influenza Vaccine

cclIV4 is an FDA-licensed vaccine approved for use in persons 6 months of age and older. This vaccine is standard clinical practice and recommended by the CDC.

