### *Safety*

Safety endpoints will be assessed using the mITT population.

Frequency and proportion of participants reporting injection site and/or systemic reactions during the first 3 days following each vaccination visit will be stratified by severity and their impact on health, and reported along with the difference in proportions reporting moderate/severe symptoms between groups and a 95% confidence interval for the difference.

Frequency and proportion of participants reporting a change in health status requiring hospital admission (including a description of the event) during the study period will be reported along with the difference in proportions between groups and a 95% confidence interval for the difference.

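### Outside the 3 days after each vaccination, serious events are captured only through a hospitalization item on a weekly online survey; there is no visit question, death capture or rule for non-responders

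*Protocol*

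**What the plan says.** Solicited reactions are surveyed about 3 days after Visit 1 in all groups and about 3 days after Visit 2 (near day 31) in groups ii and iii. Protocol 5.5.2.1 states the limit: "Participants will complete the survey a maximum of two times during the study period".

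For the rest of follow-up, Protocol 5.6 provides one safety item: "The weekly automatic electronic survey will also request participants to report the occurrence of any change in health requiring hospitalization". Protocol 5.4.1 says who answers: "Participants/participant's LAR(s) complete brief online survey regarding new ARI episodes and change in health status requiring hospitalization throughout the entire study period". Protocol 5.5.2.2 says the survey is completed online and "will be sent out each week until the end of the study period (Visit 4; day 180"). For non-response it says: "If the survey has not been completed, a reminder notification will be sent to the preferred contact method each week".

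Protocol 5.7 has sites query records for all participants up to study end. The content is documented vaccinations (5.7.1) and "documented influenza and COVID-19 infection, if recorded, from January 1, 2020 through the end of the study period" (5.7.2). Admissions and deaths are not among the listed data elements.

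The SAP's Safety paragraph in section 9.2 defines the analysis as "Frequency and proportion of participants reporting a change in health status requiring hospital admission", with a between-group difference and 95% confidence interval in the mITT population.

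**The concern.** Hospital admission is the study's only serious-event outcome (item II under E10 in SAP 3.2). Its one source is a survey that a very ill participant is less likely to complete, and that an adult who has died cannot complete. Missingness may therefore depend on the event, which would push the reported proportion down.

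The documents describe no second source, although two are within reach: participants come to the clinic for Visits 2, 3 and 4, and sites already query records to study end. A statement that concomitant vaccination raised no serious safety concern would rest on this single channel.

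**Working it through.** **1. Capture routes, set side by side**

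| Route | What it collects | Source |
|---|---|---|
| Reaction survey after Visit 1 (all groups) and Visit 2 (groups ii, iii) | Reactions, severity, impact including use of medical care | Protocol 5.5.2.1, 5.6 |
| Weekly survey to Visit 4 | ARI symptoms, test results, admission | Protocol 5.5.2.2, 5.6 |
| Visits 2, 3, 4 | Blood at each; at Visit 2 also temperature, delay criteria and any second vaccine. No health or admission question | Table 1 and step lists, Protocol 5.4.1 |
| Record query | Vaccinations; influenza and COVID-19 tests | Protocol 5.7 |
| Death or vital status | Nothing described; SAE appears only in the abbreviation lists | Protocol 2, SAP abbreviations |

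The reaction survey gets up to 3 reminders; the weekly survey, which carries the admission item, gets one reminder each week. The SAP's missing-data rule (7.2) covers immunogenicity values only.

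**2. Chances to report late**

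- Weekly surveys by day 180: 180 / 7, rounded down = 25 (days 7 to 175).
- Latest Visit 4 under the Table 1 windows: 42 + 152 + 30 = day 224, giving 224 / 7 = 32 surveys.

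One unanswered survey is therefore not a lost admission. Whether a later survey would recover it depends on the question's look-back period, and the survey forms are not in the documents.

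**3. Size, as an illustration only**

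The plan states no admission rate, response rate or sample-size basis for safety, so there is no figure to reproduce. Assume an event risk of 0.25% to 2% over follow-up and capture of 50% to 90%. Neither range comes from the documents. N = 800.

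- True events = N × risk: 800 × 0.0025 = 2 to 800 × 0.02 = 16.
- Missed = N × risk × (1 − capture): 2 × 0.1 = 0.2 to 16 × 0.5 = 8.
- At 1% risk there are 8 true events, of which 4.0 are seen at 50% capture, 5.6 at 70% and 7.2 at 90%.
- Chance of seeing no event among the 400 concomitant participants (300 + 100) at 1% risk: (1 − 0.01 × 0.5)^400 = 13.5% at 50% capture, against (1 − 0.01)^400 = 1.8% at full capture.

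**4. The safety population**

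Protocol 8.1 defines mITT as at least one vaccine received; SAP 6.2 requires both. The concomitant group receives both on day 0, so a later event cannot remove anyone from it. A sequential participant gets the second vaccine at Visit 2 (day 28 to 42). One who has an event before then and misses that vaccine leaves the SAP's safety analysis.

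Suppose a 1% risk in every group: 4/400 concomitant and 2/200 in one sequential group. If one of those 2 is dropped, the sequential proportion becomes 1/199 = 0.50%, and a true difference of 0 appears as 1.00% − 0.50% = 0.50 percentage points. With the sequential groups pooled, it is 1.00% − 3/399 = 1.00% − 0.75% = 0.25 points. The SAP does not say which groups are compared for safety.

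**The case against.** The strongest reply is that safety is the last exploratory objective, worded as descriptive, for licensed or authorized vaccines already permitted together, and that the survey is better than it first appears. Much of that stands, and it rules out several stronger readings.

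- **A reader might infer that nothing but the weekly item operates from day 4 on, and that a hospitalized participant cannot answer it.** The documents do not support this. Groups ii and iii have a second reaction survey near day 31, an LAR may answer (which matters for the 200 children), and the survey repeats weekly. Table 1 also labels the mode as phone or email and inclusion criterion vi mentions follow-up calls, although 5.5.2.2 describes online completion only.
- **A reader might infer that such a participant is counted as event-free.** The SAP does not say so. It gives no rule, and that silence is the defect.
- **A reader might infer that a severe allergic reaction treated without admission escapes the plan.** Protocol 6.3 describes such reactions as "usually occurring within a few minutes to hours after getting a dose of vaccine", which falls inside the solicited period, and that survey asks about rash and use of medical care. The event could surface, though not as a diagnosis.
- **A reader might want each named risk extracted separately.** At the protocol's own rates (1 to 2 extra Guillain-Barré cases and about 1 anaphylaxis per million), 800 participants yield 800 × 1/1,000,000 = 0.0008 to 800 × 2/1,000,000 = 0.0016 expected cases of the former and 0.0008 of the latter. Such fields are optional and would tell little.
- **The record query has limits.** It sits under headings about prior vaccination and illness, and recruitment from registries, employees, students and social media means some care will lie outside the site's system.

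None of this supplies a route for an adult death or for someone who stops responding.

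**Conclusion.** The point holds in limited form. Hospital admission rests on one self- or LAR-reported channel, with an automated reminder as the only described response to silence, no visit question and no described capture of deaths. Loss is certain only for adult deaths and for participants who stop responding; for other admissions it is a risk. E10 II may therefore be under-counted in a way that depends on the event.

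The number missed cannot be derived from the documents. The 0.2 to 8 of 2 to 16 shown above rests wholly on assumed risk and capture. Survey non-response has not been shown to differ by group, so it does not by itself establish bias in the between-group difference. The conflict between the two mITT definitions could do so, because under the SAP wording it can remove events from the sequential groups only.

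This is an inexpensive improvement to an exploratory safety endpoint. It does not bear on the primary immunogenicity analysis.

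**What to change.** 1. In Table 1 and the Visit 2, 3 and 4 step lists (Protocol 5.4.1), add one question: any hospital admission since the last visit.
2. In Protocol 5.7, add hospital admission and death, with dates from Visit 1 to Visit 4, to the query already run for all participants.
3. In SAP 3.2 and the Safety paragraph of 9.2, define E10 II as an admission found by survey, visit question or record. Report deaths. Give the proportion among participants with known status alongside the proportion on the full denominator, and define known status in advance.
4. Reconcile the mITT definitions in Protocol 8.1 and SAP 6.2, and state which one governs safety.

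**Cost:** one question at three visits already scheduled, two more items in an existing query, and slightly wider record access with matching consent, release and waiver wording. Care outside the site's health system will still depend on self-report, and the reported event rate may rise because more events are found.
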